Major exclusion criteria include, but are not limited to: receiving lipid-lowering therapy by 20 mg atorvastatin QD alone for 16 weeks is medically contraindicated or inappropriate based on opinion of investigator; heart failure of New York Heart Association (NYHA) class III or IV or last known left ventricular ejection fraction < 30%; type 1 diabetes or poorly controlled type 2 diabetes; systolic blood pressure (SBP) > 160 mmHg or diastolic BP (DBP) > 100 mmHg; previously received evolocumab or any other investigational therapy to inhibit proprotein convertase subtilisin/kexin type 9 (PCSK9); unwillingness or inability to discontinue until end of study the following: red yeast rice, niacin (> 200 mg/day), > 1000 mg/day omega-3 fatty acids, and all prescription lipid-regulating drugs except study-provided atorvastatin; any of the following drugs in the last 2 months: systemic cyclosporine, systemic steroids, vitamin A derivatives and retinol derivatives for the treatment of dermatologic conditions (eq, Accutane), or a cholesterylester transfer protein (CETP) inhibitor in the last 12 months. Female subjects cannot be pregnant, breast feeding, planning to become pregnant, or planning to breastfeed and premenopausal females must have to be willing to use (an) acceptable method(s) of effective birth control during treatment with investigational product (evolocumab or placebo) and for an additional 15 weeks after the end of treatment with investigational product (evolocumab or placebo).

For a full list of eligibility criteria, please refer to Section 4.1.1 and Section 4.1.2.

Investigational Product

Amgen Investigational Product Dosage and Administration: Evolocumab and placebo SC will be administered using a spring-based prefilled AI/Pen or by 3.5 mL Personal Injector. Each prefilled AI/Pen will contain 1.0 mL deliverable volume; each Personal Injector will contain 3.5 mL deliverable volume.

Evolocumab will be administered at 1 of 2 regimens:

Evolocumab 140 mg SC Q2W by prefilled AI/Pen or

Evolocumab 420 mg SC QM by 3.5 mL Personal Injector

Placebo will be administered at 1 of 2 regimens:

Placebo SC Q2W by prefilled Al/Pen or

Placebo SC QM by 3.5 mL Personal Injector.

Non-Amgen Non-investigational Product Dosage and Administration: Atorvastatin 20 mg will be provided by Amgen.

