- 210 Treatment in the last 2 months prior to screening and lipid stabilization assessments with any of the following drugs: systemic cyclosporine, systemic steroids (eg, intravenous [IV], intramuscular [IM], or oral [PO] administration), vitamin A derivatives and retinol derivatives for the treatment of dermatologic conditions (eg, Accutane); (Note: vitamin A in a multivitamin preparation is permitted).
- 211 Hyperthyroidism or hypothyroidism as defined by thyroid stimulating hormone (TSH) below the lower limit of normal (LLN) or > 1.5 times the upper limit of normal (ULN), respectively, at screening.
- 212 Moderate to severe renal dysfunction, defined as an estimated glomerular filtration rate (eGFR) < 30 mL/min/1.73m² at screening.
- 213 Persistent active liver disease or hepatic dysfunction, defined as aspartate aminotransferase (AST) or alanine aminotransferase (ALT) > 2 times the ULN as determined by central laboratory analysis at screening or lipid stabilization assessments.
- 214 Creatine kinase (CK) > 3 times the ULN at screening or lipid stabilization assessments.
- 215 Known active infection or major hematologic, renal, metabolic, gastrointestinal or endocrine dysfunction (except diabetes).
- 216 Deep vein thrombosis or pulmonary embolism within 3 months prior to randomization.
- 217 Female subject who has either (1) not used (an) acceptable method(s) of effective birth control (see below) for at least 1 month prior to screening and (2) is not willing to inform her partner of her participation in this clinical study and to use such (an) acceptable method(s) of effective birth control during treatment with IP (evolocumab or placebo) and for an additional 15 weeks after the end of treatment with IP (evolocumab or placebo), unless the female subject is permanently sterilized or postmenopausal (see below);

- A female is considered of childbearing potential unless **permanently** sterilized or postmenopausal with menopause defined as:
 - 12 months of spontaneous and continuous amenorrhea in a female
 ≥ 55 years old, or
 - 12 months of spontaneous and continuous amenorrhea with a follicle-stimulating hormone (FSH) level > 40 IU/L (or according to the definition of "postmenopausal range" for the laboratory involved) in a female < 55 years old
 - unless the subject has undergone bilateral oophorectomy

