- acceptable methods of preventing pregnancy include not having intercourse, (true sexual abstinence), surgical contraceptive methods - (vasectomy of the male partner or bilateral tubal ligation/occlusion), use of hormonal birth control methods (pills, shots/injections, implants, or patches), intrauterine devices (IUDs), or two (2) barrier methods (each partner must use one barrier method) and at least one of the barrier methods must include spermicide - males must use a condom with spermicide; females must choose either a diaphragm with spermicide, OR cervical cap with spermicide, OR contraceptive sponge with spermicide. Note: a male and female condom cannot be used together due to the risk of tearing.
 - Note: If additional medications are given during treatment which may alter the contraceptive requirements (these additional medications may require an increase in the number of contraceptive methods and/or length of time that contraception is to be utilized after the last dose of protocol-required therapies) the investigator is to discuss these changes with the study subject.
- 218 Subject is pregnant or breast feeding, or planning to become pregnant or planning to breastfeed during treatment with IP (evolocumab or placebo) and/ or within 15 weeks after the end of treatment with IP (evolocumab or placebo).
- 219 Malignancy (except non-melanoma skin cancers, cervical in-situ carcinoma, breast ductal carcinoma in situ, or stage 1 prostate carcinoma) within the last 5 years prior to screening.
- 220 Subject has previously received evolocumab or any other investigational therapy to inhibit PCSK9.
- 221 Currently receiving treatment in another investigational device or drug study, or less than 30 days since ending treatment on another investigational device or drug study(s) or planning to receive other investigational procedures while participating in this study.
- 222 Subject has known sensitivity to any of the active substances or their excipients to be administered during dosing, eg, carboxymethylcellulose, or atorvastatin.
- 223 Subject likely to not be available to complete all protocol-required study visits or procedures, or unreliability as a study participant (eg, alcohol or other drug abuse in the past year or psychosis), to the best of the subject's and Investigator's knowledge.
- History or evidence of any other clinically significant disorder, condition or disease that, in the opinion of the Investigator or Amgen physician, if consulted,

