5. SUBJECT ENROLLMENT

Before subjects begin participation in any study-specific activities/procedures, Amgen requires a copy of the site's written institutional review board (IRB) approval of the protocol, informed consent form (ICF), and all other subject information and/or recruitment material, if applicable (see Section 11.2). All subjects must personally sign and date the consent form before commencement of study-specific procedures. SAEs, **ADEs**, and study-related AEs will be collected upon signing the informed consent form.

A subject is considered enrolled when the investigator decides that the subject has met all eligibility criteria assessed at screening. The investigator is to document this decision and date, in the subject's medical record and in/on the enrollment eCRF.

Each subject who enters into the screening period for the study (defined as signing the informed consent form) receives a unique subject identification number before any study-related activities/procedures are performed. The subject identification number will be assigned by interactive voice response system or interactive web response system (IVRS/IWRS). This number will be used to identify the subject throughout the clinical study and must be used on all study documentation related to that subject.

The subject identification number must remain constant throughout the entire clinical study; it must not be changed after initial assignment, including if a subject is rescreened.

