8.3 Reasons for Removal From Screening, Lipid Stabilization, Treatment, or Study

8.3.1 Reasons for Removal From Screening or Lipid Stabilization

Reasons for removal from screening or lipid stabilization include any of the following:

- subject request
- safety concern (eg, due to an adverse event, failure to follow contraception, pregnancy, breast feeding, and/or atorvastatin withholding requirements)
- decision by sponsor (other than subject request or safety concern)
- death
- lost to follow-up

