8.3.2 Reasons for Removal From Treatment

Reasons for removal from protocol-required investigational products or procedural assessments include any of the following:

- subject request
- safety concern (eg, due to an adverse event, failure to follow contraception, pregnancy, breast feeding, and/or protocol requirements)
- death
- lost to follow-up
- decision by Sponsor (other than subject request, safety concern, lost to follow-up)

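### Exclusion 217 joins its two limbs with *and*: read literally, it does not bar a woman who used contraception before screening but will not use it on treatment, contrary to the synopsis

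*Protocol*

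**What the plan says.** **Exclusion 217 (Protocol 4.1.2).** For women who are neither permanently sterilized nor postmenopausal, the sentence opens with *either* and has two limbs. Limb (1) is not having used acceptable contraception. The text then runs "for at least 1 month prior to screening and (2) is not willing to inform her partner of her participation in this clinical study", and limb (2) continues with use of such contraception during IP and for 15 weeks after it ends. The word joining the limbs is *and*. The replacement text in the Amendment 3 summary carries the same *and*, so this is not a fault of text extraction.

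**Synopsis (major exclusion criteria).** "premenopausal females must have to be willing to use (an) acceptable method(s) of effective birth control during treatment with investigational product", and for the same 15 weeks after. Nothing ties this to what she did before screening. The synopsis then adds: "For a full list of eligibility criteria, please refer to Section 4.1.1 and Section 4.1.2".

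**Section 5.** "A subject is considered enrolled when the investigator decides that the subject has met all eligibility criteria assessed at screening".

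**Related provisions.**
- Within 217, "acceptable methods of preventing pregnancy include not having intercourse", so abstinence counts as contraception.
- Exclusion 218 covers a woman who is pregnant or breastfeeding, or "planning to become pregnant or planning to breastfeed during treatment with IP (evolocumab or placebo") or in the 15 weeks after.
- Section 8.3.1 lists as a ground for removal before randomization a "safety concern (eg, due to an adverse event, failure to follow contraception, pregnancy, breast feeding, and/or atorvastatin withholding requirements"). Section 8.3.2 lists on treatment a "safety concern (eg, due to an adverse event, failure to follow contraception, pregnancy, breast feeding, and/or protocol requirements").

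**Exclusion 206 (secondary).** The HbA1c limb requires a value above 10.0% at screening and at lipid stabilization. Table 1 marks HbA1c at Screen and W12 only.

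**The concern.** 217 is the only criterion in Section 4.1 that deals with willingness to use contraception, and sites enroll on those criteria. *Either* signals alternatives, while *and* requires both limbs, so the sentence supports two different rules. Under the literal one, a woman who refuses contraception on treatment passes 217 if she used it in the month before screening. The synopsis bars her. What is at stake is protection against pregnancy during exposure to the study drug, and sites applying one rule.

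For 206, a subject with a screening HbA1c above 10.0% meets the limb only if a second value exists, and no second value is scheduled before randomization. Two sites could treat the same screening result differently.

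**Working it through.** No published figure is involved. The check sets out the logic of 217 against the synopsis.

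**Inputs.** Three yes/no facts about a woman of childbearing potential: prior use (acceptable contraception for at least 1 month before screening), inform (willing to tell her partner), use (willing to use contraception on IP and for 15 weeks after).

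**Rules.**
- Limb (1) = no prior use.
- Limb (2) = not (inform and use).
- 217 by its connective = (1) and (2).
- 217 by *either* = (1) or (2).
- Synopsis = not use.

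| Row | Prior use | Inform | Use | 217 *and* | 217 *or* | Synopsis |
|---|---|---|---|---|---|---|
| 1 | yes | yes | yes | in | in | in |
| 2 | yes | yes | no | **in** | out | **out** |
| 3 | yes | no | yes | in | out | in |
| 4 | yes | no | no | **in** | out | **out** |
| 5 | no | yes | yes | in | out | in |
| 6 | no | yes | no | out | out | out |
| 7 | no | no | yes | out | out | in |
| 8 | no | no | no | out | out | out |
| Excluded | | | | 3 of 8 | 7 of 8 | 4 of 8 |

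**Results.**
- Of the 4 profiles that the synopsis excludes, the *and* reading lets in 2 (rows 2 and 4).
- Holding the partner informed (rows 1, 2, 5, 6), *and* excludes 1 of 4, the synopsis 2 and *or* 3. *And* contradicts the synopsis in row 2. The two readings of 217 differ in rows 2 and 5.
- Where 217 excludes and the synopsis does not, there is no contradiction, because the synopsis says that its list is not limited to what it names.

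**Does the parsing of limb (2) matter?** Suppose limb (2) means refusing both to inform and to use, which is true only in rows 4 and 8. Then *and* excludes row 8 alone (1 of 8). Rows 2 and 4 still get in, because limb (1) is false for any prior user. Under this parse *or* excludes rows 4 to 8 (5 of 8) and also misses row 2. Changing *and* to *or* would therefore not settle the criterion by itself.

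**206.** Values required: 2. Values scheduled before randomization: 1 (Screen). Section 7.2.1.2 also lists HbA1c once, with the screening bloods. Table 1 marks fasting lipids and chemistry at End of Lipid Stabil, but Table 2 places HbA1c under other labs, not chemistry.

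**The case against.** The strongest reply is that the documents largely show what was meant. *Either* introduces alternatives, the synopsis makes willingness mandatory, and the removal rules treat failure to follow contraception as a safety ground with no link to prior use. Only the bare connective points the other way. A pointer to a fuller list in 4.1.2 adds criteria and need not cancel one already stated. All of this stands, and it lowers the weight of the point. It does not correct the operative sentence, to which the synopsis itself sends the site.

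There are also safeguards. Exclusion 218 bars planned pregnancy. Exclusion 223 (unreliable participant) could be applied to a woman who says she will not comply. Table 1 schedules serum pregnancy tests at Screen, End of Lipid Stabil and W12, and urine tests at D1, W2 and W8: 3 + 3 = 6. Section 9.3 has investigators monitor for pregnancy through 15 weeks after IP. Abstinence qualifies as contraception, so few women may be affected. These reduce the risk, but none makes unwillingness a bar to entry: 218 does not reach a woman who plans no pregnancy, 223 does not name contraception, and tests detect a pregnancy rather than prevent it. Consent pages were removed from the reviewed copy, so what they say about contraception is unknown.

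A reader might infer that the sponsor meant to drop the bar, or that women refusing contraception will be enrolled. The documents support neither. The surrounding text points to the opposite intention, and many sites may well apply *or*.

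On 206, a reader might infer that the HbA1c limb can never be met. That goes too far: Section 7.2.1.4 permits retesting during screening, and Section 7.6 allows a scheduled blood sample to be analyzed for any protocol test. Nor does the *or* in 213 and 214 prove a slip in 206, since 210 also uses *and* for the same two assessments.

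**Conclusion.** The point holds as a narrow drafting error in an operative safety criterion. By its connective, 217 admits a woman whom the synopsis bars: one profile in four with the partner informed, two in eight overall. These are counts of logical cases, not of subjects; the documents give no basis for estimating how many women are concerned. The conclusion assumes only that a site may apply the sentence as written, and it does not depend on how limb (2) is parsed. The likely intention is clear enough that this is a minor correction. Sample size, power, alpha and the planned analyses are unaffected.

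The 206 mismatch is real but secondary: the second HbA1c value is permitted, not scheduled, so meeting the limb depends on a site's choice.

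**What to change.** **217.** Replace the two-limb sentence with separate exclusions. A woman of childbearing potential is excluded if
- (a) she is unwilling to use acceptable, effective contraception while on IP and for 15 weeks afterwards, **or**
- (b) she is unwilling to tell her partner that she is taking part.

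Then state in its own sentence whether lack of acceptable contraception for at least 1 month before screening also excludes. Limb (a) alone excludes rows 2, 4, 6 and 8 and so matches the synopsis in all 8 rows. Limb (b) keeps the partner element already in 217 and goes beyond the synopsis by adding rows 3 and 7 (4 + 2 = 6 of 8). Listing the two refusals separately also removes the doubt over a negation that covers two joined items.

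**206.** Mark HbA1c at End of Lipid Stabil in Table 1 for subjects whose screening value is above 10.0%. This leaves the two-value rule as it is.

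**Cost.** One wording amendment, with the investigator agreement and IRB/IEC approval that Section 12.1 requires, at approximately 100 sites (Section 3.2). It can go into the next amendment. The 217 change needs no visit, sample or procedure. The 206 change adds one HbA1c for a subset of subjects at a visit where blood is already drawn; the documents do not say whether it needs its own tube. Neither changes the analyses.

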6. TREATMENT PROCEDURES

6.1 Classification of Products and/or Medical Devices

The Amgen investigational products used in this study include: evolocumab and matching placebo.

The non-Amgen non-investigational products used in this study include: atorvastatin 20 mg.

The Investigational Product Instruction Manual (IPIM), a document external to this protocol, contains detailed information regarding the storage, preparation, **destruction**, and administration of evolocumab, matching placebo, and atorvastatin.

The medical devices used in this study include: prefilled autoinjector/pen and 3.5 mL Personal Injector.

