6.7 Medical Devices

IP will be provided by prefilled Al/pen for Q2W administration and by 3.5 mL Personal Injector for QM administration (Section 6.2.1). The prefilled Al/pen is a modified version of the SureClick[™] autoinjector, a device that is commercially available for the administration of Aranesp[®] or Enbrel[®] drug product by patients or caregivers in a non-healthcare environment, or by healthcare professionals in the clinic environment in the United States (Enbrel[®] only) and in Europe. The 3.5 mL Personal Injector is a novel single-use, disposable injector with prefilled cartridge assembly that delivers 3.5 mL of

evolocumab to subcutaneous tissue over a period of several minutes (less than 10 minutes).

Medical devices (eg, syringes, sterile needles, alcohol prep pads), that are commercially available are not usually provided or reimbursed by Amgen (except, for example, if required by local regulation). The investigator will be responsible for obtaining supplies of these devices.

6.8 **Product Complaints**

A product complaint is any written, electronic or oral communication that alleges deficiencies related to the identity, quality, durability, reliability, safety, effectiveness, or performance of a drug(s) or device(s) after it is released for distribution to market or clinic by either Amgen or by distributors and partners for whom Amgen manufactures the material. This includes any drug(s) or device(s) provisioned and/or repackaged/modified by Amgen. Drug(s) or device(s) includes investigational product.

Any product complaints associated with the prefilled Al/Pen, the 3.5 mL Personal Injector, or other Amgen provided, protocol-required product (ie, atorvastatin) in this study must be reported to Amgen. Please do not use the device or product that is subject of a complaint until Amgen confirms that it is permissible to do so.

Examples of product complaints that need to be reported to Amgen include, but are not limited to:

- broken or cracked containers
- subject or healthcare provider cannot appropriately use the product despite training (eg, due to malfunction of the Al/Pen or 3.5 mL Personal Injector)
- missing labels, illegible labels, incorrect labels, and/or suspect labels
- change in IP appearance, for example color change or visible presence of foreign material
- unexpected quantity or volume, for example number of tablets or amount of fluid in the prefilled AI/Pen or 3.5 mL Personal Injector

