9.3 Pregnancy and Lactation Reporting

If a pregnancy occurs in a female subject, or female partner of a male subject, while the subject is taking protocol-required therapies report the pregnancy to Amgen as specified below.

In addition to reporting any pregnancies occurring during the study, investigators should monitor for pregnancies that occur after the last dose of protocol-required therapies through 15 weeks after the end of treatment with IP.

The pregnancy should be reported to Amgen **Global Patient Safety** within 24 hours of the investigator's knowledge of the event of a pregnancy. Report a pregnancy on the Pregnancy Notification Worksheet (Appendix C).

If a lactation case occurs while the female subject is taking protocol-required therapies report the lactation case to Amgen as specified below.

In addition to reporting a lactation case during the study, investigators should monitor for lactation cases that occur after the last dose of protocol-required therapies through 15 weeks after the end of treatment with IP.

Any lactation case should be reported to Amgen **Global Patient Safety** within 24 hours of the investigator's knowledge of event. Report a lactation case on the Lactation Notification Worksheet (Appendix C).

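### Exclusion 217 and the synopsis start the contraception commitment only with IP, so at least 28 days of study atorvastatin carry no stated requirement

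*Protocol*

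**What the plan says.** Exclusion 217 has two limbs. The first looks back and the second looks forward, and they are joined as follows: "not used (an) acceptable method(s) of effective birth control (see below) for at least 1 month prior to screening and (2) is not willing". The forward limb asks for "acceptable method(s) of effective birth control during treatment with IP (evolocumab or placebo) and for an additional 15 weeks" after IP treatment ends. The synopsis requires premenopausal women to be willing to use "acceptable method(s) of effective birth control during treatment with investigational product (evolocumab or placebo") and for the same 15 weeks afterwards. The planning limb of exclusion 218 is also tied to IP treatment.

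Atorvastatin is not IP. Section 6.1 states: "The non-Amgen non-investigational products used in this study include: atorvastatin 20 mg". Under Section 7.2.1.2 and Table 1 footnote a, it starts at enrollment and is taken every day for at least 4 weeks before randomization. Day 1 is the first administration of IP.

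Other sections use a wider term than IP:

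- Section 6.8 refers to "other Amgen provided, protocol-required product (ie, atorvastatin").
- Section 9.3 says that if a pregnancy occurs "while the subject is taking protocol-required therapies report the pregnancy to Amgen as specified below", which means within 24 hours.
- The note in 217 on added medications refers to the "length of time that contraception is to be utilized after the last dose of protocol-required therapies".
- Section 8.3.1 gives as safety reasons for removal from screening or lipid stabilization "failure to follow contraception, pregnancy, breast feeding, and/or atorvastatin withholding requirements".

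Exclusion 208 already runs its own requirement from the start of lipid stabilization.

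**The concern.** A woman of childbearing potential can take a protocol-required drug every day through the run-in without any criterion asking her to use contraception. Section 8.3.1 lets a site remove her for failing to follow contraception, but no criterion says what she had to follow before Day 1. The removal rule and the eligibility rule do not fit together.

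Two features of the wording widen the gap. A woman who stops during the run-in, as Section 7.2.1.2 directs for atorvastatin intolerance, never receives IP, so her forward window is empty. And because both limbs of 217 must apply before it excludes, a woman who used contraception in the month before screening stays eligible under 217 even if she declines it from then on. The synopsis, which asks for willingness without that condition, says otherwise.

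An unplanned pregnancy in the run-in would be found only after exposure. This is a matter of participant safety and consistent eligibility decisions across sites, not of inference.

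**Working it through.** **Inputs**

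- Lipid stabilization: at least 4 weeks (Table 1 footnote a; 7.2.1.2). A week is 7 days (7.2).
- Treatment period: 12 weeks.
- Consent to randomization: 8 weeks (7.2.1). Randomization to Day 1: at most 5 days (7.2.1.3).
- Last planned IP dose: week 8 for QM, week 10 for Q2W (synopsis, Procedures).
- Tail after IP: 15 weeks (217).
- Pregnancy tests before IP: serum at screening, serum at end of stabilization, urine on Day 1 (Table 1).

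**The plan's own figures reproduce.** Exclusion 201 gives about 16 weeks of atorvastatin: 4 + 12 = 16. Section 3.5.1 gives maximum durations of 20 and 22 weeks: 8 + 12 = 20 (QM) and 8 + 14 = 22 (Q2W).

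**Requirement by period**

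| Period | Study drug | Contraception required by a criterion |
|---|---|---|
| At least 1 month before screening | None | Limb (1), past use only |
| Screening to first atorvastatin dose | One placebo injection | None |
| First atorvastatin dose to Day 1 | Atorvastatin daily | None |
| Day 1 to end of IP treatment | IP and atorvastatin | Limb (2) |
| Next 15 weeks | Atorvastatin until the week 12 visit | Limb (2) |

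The screening placebo injection does not open the forward window, because Day 1 is defined as the first IP administration and comes later.

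**Size of the gap**

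- Atorvastatin before Day 1: 4 × 7 = 28 days at least.
- Share of the minimum course: 28 / (28 + 84) = 28 / 112 = 25.0%.
- Consent to Day 1: 8 × 7 + 5 = 61 days at most, so atorvastatin before Day 1 lies between 28 days and somewhat under 61.
- First atorvastatin dose to the next scheduled pregnancy test: at least 28 days.
- Woman who leaves before IP: forward commitment of 0 weeks.

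**Length of the commitment, counted to 15 weeks after the last planned IP dose**

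- QM now: 8 + 15 = 23 weeks. With the minimum run-in: 23 + 4 = 27 weeks (4/23 = 17.4% longer).
- Q2W now: 10 + 15 = 25 weeks. With the minimum run-in: 25 + 4 = 29 weeks (4/25 = 16.0% longer).
- If treatment is instead taken to end at about week 12, following the glossary's definition of end of treatment: 12 + 15 = 27 weeks, rising to 31 in both regimens (4/27 = 14.8%).

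**The joined limbs.** Suppose a woman used contraception before screening but will not commit to it afterwards. Limb (1) is false and limb (2) is true. Joined by and, the exclusion is false, so she is eligible under 217. Under the synopsis sentence she is not.

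**The case against.** The strongest reply is that the documents never say atorvastatin needs contraception. That would be in the package insert or the product manual, neither of which is available here. On this view a window tied to IP in 217, 218, the synopsis and the follow-up part of 9.3 is a consistent choice. Reporting under 9.3 does not imply a duty, since it also covers partners of male subjects, from whom no contraception is asked. The note in 217 concerns added medicines and an end date. Controls also exist: 201 covers the whole atorvastatin course by investigator judgement, 218 excludes pregnancy, all criteria are rechecked before randomization, and three pregnancy tests come before or on Day 1.

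Part of this stands. Sections 9.3, 6.8 and the note in 217 are only supporting evidence. For women already taking a statin, the run-in is not a first statin exposure. The repair does not speed up detection, and the schedule already has a longer gap on IP: week 2 to week 8 is 6 × 7 = 42 days. Section 3.5.1 leaves no room for the 5-day lag, so 56 days is the alternative to 61, and the 8-week limit is worded as a recommendation.

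The rest does not close the gap. Section 8.3.1 applies contraception to the run-in by name and treats failure there as a safety concern, so the premise comes from the protocol itself. Exclusion 201 and Section 8.2 give discretion, and the tests and 218 detect or exclude a pregnancy. None of them requires prevention.

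**Conclusion.** The concern holds. As written, no eligibility criterion requires contraception between screening and Day 1, a period that includes at least 28 days of study atorvastatin (25.0% of the minimum 112-day course). Exclusion 217 read literally also admits women whom the synopsis would exclude. Following the rule as written gives the wrong eligibility result, so this is more than missing detail, and it should be corrected.

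The conclusion rests on reading IP as evolocumab or placebo, as the protocol defines it, and on the protocol's own treatment of contraception in Section 8.3.1. It describes time without a stated duty, not time known to be unprotected; many women who meet the look-back requirement would probably continue. The number of women of childbearing potential is not given, and the removed consent pages may contain instructions, so confidence is medium. Power, alpha and the efficacy analysis are unaffected.

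**What to change.** In 217 and in the synopsis sentence, require effective birth control from the first dose of study-provided atorvastatin (the start of lipid stabilization), through IP treatment, and for 15 weeks after it ends. For women who never receive IP, require it through the last dose of study-provided atorvastatin. In 217, also state that limb (2) excludes by itself, whether or not limb (1) applies; without this, the new start date would not bind women who used contraception before screening. Align the planning limb of 218 for consistency only. Sections 8.3.1 and 9.3 can stay as they are.

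The cost is a start date, an end date and one clause in 217, the same dates in the synopsis, and a matching edit in 218. No visit or test is added. Participants commit for at least 4 more weeks, and women who used contraception before screening but will not commit to it afterwards would be excluded; their number is not given.
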